9.1.2 Serious Adverse Events

An SAE is any untoward medical event that occurs at any dose from the time of study drug administration and continuing until 30 days after the last dose that:

- results in death
- is life-threatening (patient is at immediate risk of death from the event as it occurred)¹
- requires inpatient hospitalization (formal admission to a hospital for medical reasons) or prolongation of existing hospitalization ²
- results in persistent or significant disability/incapacity ³
- results in a congenital anomaly/birth defect
- is an important medical event ⁴
- ¹ "Life-threatening" means that the patient was at immediate risk of death at the time of the SAE; it does not refer to a SAE that hypothetically might have caused death if it were more severe.
- ² This means that hospital inpatient admission or prolongation of hospital stay was required for the treatment of the AE, or that one or the other occurred as a consequence of the event. Hospitalizations for elective surgery or other medical procedures that are not related to a TEAE are not considered SAEs. The planned overnight hospitalization on Day 1 of Cycle 1 is exempt from this definition and is not considered an SAE since it is a study procedure and not for treatment of an SAE, unless an AE occurs during the hospitalization that meets the criteria above.
- ³ "Persistent or significant disability or incapacity" means a permanent or significant and substantial disruption of a person's ability to carry out normal life functions.
- ⁴ Important medical events that may not result in death, are not life-threatening, or do not require hospitalization may be considered SAEs when, based on appropriate medical judgment, they may jeopardize the patient and may require medical or surgical intervention to

prevent one of the outcomes listed in this definition. Examples of such events include allergic bronchospasm requiring intensive treatment in an emergency room or at home, blood dyscrasias or convulsions that do not result in inpatient hospitalization, or the development of drug dependency or drug abuse.

Medical and scientific judgment should be exercised in deciding whether expedited reporting is appropriate in situations where none of the outcomes listed above occurred. Important medical events that may not be immediately life-threatening or result in death or hospitalization but may jeopardize the patient or may require intervention to prevent one of the other outcomes listed in the definition above should also usually be considered serious.

All other AEs are considered non-serious. All non-serious AEs will be followed to resolution, or until the study ends, and reported to the sponsor as requested, to the Institutional Review Boards (IRBs)/Institutional Ethics Committees (IECs) according to IRB/IEC policies (to include annual Continuing Review Reports), to the CRC as required, and to the U.S. Food and Drug Administration (FDA) as required for the annual report.

AEs meeting the stopping criteria outlined in Section 7 of this protocol will be reported to the sponsor, the IRBs/IECs, and the CRC following the SAE reporting guidelines.

Management of all AEs including hypersensitivity or hyperimmune reactions will be managed by treating physicians in conjunction with relevant institutional guidelines and with the consultation of the sponsor's medical monitor.

9.1.3 Adverse Event by Severity or Intensity

The assessment of severity of an AE will be rated according to the criteria in Table 6.

Grade 1 (Mild)	Mild; asymptomatic or mild symptoms; clinical or diagnostic observations only; intervention not indicated. The adverse event (AE) does not interfere with routine activities. The patient may experience slight discomfort.	
Grade 2 (Moderate)	Moderate; minimal, local or noninvasive intervention indicated; The AE interferes with routine activities. The patient may experience significant discomfort.	
Grade 3 (Severe)	Severe or medically significant but not immediately life-threatening; hospitalization or prolongation of hospitalization indicated. The patient is unable to perform routine activities. The patient may experience intolerable discomfort or pain.	
Grade 4 (Life-Threatening)	Life-threatening consequences; urgent intervention indicated.	
Grade 5 (Fatal)	Death related to AE	

Table 6Definitions of Adverse Events Severity

Based on the Common Terminology Criteria for Adverse Events v 5.0 (CTCAE).

The term "severe" is used to describe the intensity of an AE; the event itself could be of relatively minor clinical significance (e.g., 'severe' headache). This is not the same as "serious".

Seriousness of AEs is based on the outcome of an AE and usually associated with events that pose a threat to a patient's life or functioning.

9.1.4 Relationship between Adverse Events and Study Drug

Determination of the relationship (if any) between the AE and the study drug will be made using the guidelines presented in Table 7.

Table 7Guidelines for Determining the Relationship (if any) Between Adverse Event and
the Study Drug

Definitely Related:	This causal relationship is assigned if the AE starts a reasonable time after the administration of study drug, stops/improves when the study drug is stopped, and could reasonably be explained by known characteristics of the study drug.
Probably Related:	This causal relationship is assigned when the AE starts a reasonable time after the administration of study drug, stops/improves when the study drug is stopped, and could not be reasonably explained by known characteristics of the patient's clinical state.
Possibly Related:	This causal relationship is assigned when the AE starts a reasonable time after the administration of study drug, but could be produced by the patient's clinical state or other modes of therapy administered to the patient.
Unlikely Related	This causal relationship is assigned when the time association or the patient's clinical state is such that the study drug was not likely to have had an association with the observed AE.
Not Related:	This causal relationship is assigned when there is clearly no evidence of association with the study drug and the observed AE.

Pregnancy or lactation are exclusion criteria for this study. Pregnancy per se is not considered an AE unless there is cause to believe that the investigational drug may have interfered with the effectiveness of a contraceptive medication. Refer to Section 4.4 for details.

9.1.5 Adverse Event Follow-up

All AEs occurring during the study are to be followed up in accordance with good medical practice until they are resolved, stabilized or judged no longer clinically significant or, if a chronic condition, until fully characterized. Any AEs that are considered drug-related (possibly related, probably related, or definitely related) must be followed until resolution or until stabilization.

All unresolved AEs following the study should be followed by the investigator until the events are resolved, the patient is lost to follow-up, or the AE is otherwise explained. At the last scheduled visit, the investigator should instruct each patient to report any subsequent event(s) that the patient, or the patient's personal physician, believes might reasonably be related to participation in this study.

Prior to the conclusion of the study at the site, the investigator should notify the ImmuneSensor Therapeutics (ImmuneSensor), Safety Associate, or designee of any death or AE occurring at any time after a patient has discontinued or terminated study participation that may reasonably be related to this study. After study conclusion, the investigator should notify ImmuneSensor of any death or AE they are aware of occurring at any time after a patient has discontinued or terminated study participation that may reasonably be related to this study.

The investigator should notify ImmuneSensor or its designee, of any death or AE occurring at any time after a patient has discontinued or terminated study participation that may reasonably be related to this study.

9.1.6 **Overdose**

Any dosing errors should be immediately reported to the sponsor. The dosing error should be fully documented in the patient's source documentation/case report form (CRF) and where applicable, filed promptly with IRB and regulatory authorities.

Subsequent dosing shall be discontinued until the investigator and sponsor have both determined it's safe to resume treatment.

9.1.7 **Pregnancies**

No clinical data on the effects on pregnancy or lactation are available. Precautions relative to patients of reproductive potential are discussed in Section 4.4.

9.2 SERIOUS ADVERSE EVENT REPORTING

9.2.1 **Reporting Requirements**

Any SAE made known to the investigator must be reported by the investigator if it occurs during the clinical study, whether or not the SAE is considered to be related to the IMSA101 treatment. An SAE report consists of the SAE form, the AE form, and the concomitant medication form.

A copy of these forms must be forwarded within 24 h of awareness. Contact details will be provided in the study reference manual.

The investigator should not wait to receive additional information to document fully the event before notification of an SAE, though additional information may be requested. Where applicable, information from relevant laboratory results, hospital case records, and autopsy reports should be obtained.

Instances of death, congenital abnormality, or an event that is of such clinical concern as to influence the overall assessment of safety, if brought to the attention of the investigator at any time after cessation of study drug administration and linked by the investigator to this study, should be reported to the medical monitor.

Progression of disease by itself is not considered an AE but rather an expected outcome and a study endpoint and should not be reported as AEs or SAEs, unless it results in hospitalization or death. AEs associated with progressive disease (such as a pleural effusion or gastrointestinal obstruction) and associated hospitalizations to treat the AE or SAE are reportable events.

10 STATISTICAL METHODS

10.1 GENERAL CONSIDERATIONS

10.1.1 Statistical and Analytical Plans

A formal detailed statistical analysis plan (SAP) will be created prior to the analysis of any data.

The purpose of the Phase I dose escalation study is to determine the safety and tolerability of IMSA101 and to define the MTD/RP2D of the drug when administered by intratumoral injection. Groups of 3 to 6 patients will be treated at each dose level until the MTD is reached as detailed in Section 3.1. All patients meeting the eligibility criteria and receiving at least 1 dose of IMSA101 will be evaluable for safety in the Safety Population.

Phase IIA statistics will be mainly descriptive and informed by the ultimate selection of tumor types to be evaluated. Statistical methods including pre-defined criteria for signal detection and drug differentiation from standard-of-care benchmarks as well as stage progression and futility assessment will be included in the final SAP.

10.1.2 **Disposition of Patients**

A tabulation of patient disposition will be presented, including the number in each analysis population, the number lost to follow-up, the number that withdrew prior to completing the study, and reason(s) for withdrawal.

10.1.3 Blinding and Randomization

This clinical study is open-label and non-randomized.

10.2 ANALYSIS DATASETS

10.2.1 Safety Population

The safety population will consist of all patients receiving at least 1 dose of study medication.

10.2.2 **Definition of Study Cycles**

Each treatment cycle will be 4 weeks (28 days) in duration. There will be 3 clinic visits in Cycle 1 (Day 1, on Day 8, and Day 15). Thereafter for all other cycles, there will be 2 clinic visits on Day 1 and Day 15. Study drug will be administered at all visits following screening except the EOT and EOS visits.

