RECIST v1.1 criteria do not mention including or excluding lesions that are being biopsied or injected. However, for the purposes of this protocol, the injected and biopsied lesions are to be captured as non-target lesions only (Phase I only), as follows:

- Injected and biopsied lesion = non-target lesion #1
- Non-injected and biopsied lesion = non-target lesion #2 (if applicable)

See Schedule of Assessments and Study Activities (Table 1 and Table 2) for details.

3.1.1 **Phase I – Dose Escalation Plan**

The Phase I dose escalation is illustrated in Figure 8 for monotherapy and Figure 9 and Figure 10

for combination therapy.

Phase I Dose Escalation – Monotherapy:

- Each dose escalation cohort will initially recruit at least 3 patients in a standard 3+3 design. To proactively ensure at least 3 patients are considered evaluable, a fourth patient may be enrolled and treated in addition to the initial 3 patients in each cohort (the fourth patient may only be enrolled if they are identified at the time the third patient slot is being filled).
- Dose escalation design in which administered dose levels will be escalated stepwise in successive cohorts of 3 to 6 (NOTE: 7 if fourth slot is filled and a single DLT is identified among the first 4 patients) patients per dose group until the RP2D or MTD level is identified.
- The first patient enrolled in each dose level must complete the first two weeks of Cycle 1 prior to enrolling the second and third (fourth when applicable) patients.
- Dose levels to be evaluated include (although not necessarily limited to) 100 µg (representing 1/60th of the pre-clinical HNSTD dose), 200 µg, 400 µg, 800 µg, and 1,200 µg.
- IMSA101 will initially be administered by intratumoral injections on Day 1 of Weeks 1, 2, and 3 for Cycle 1 (i.e., weekly dosing 3 out of 4 weeks), and on Day 1 of Weeks 1 and 3 (i.e., bi-weekly dosing) for all cycles thereafter.
- No dose escalation decisions will be made until all patients in a dose level complete the first 28 days of treatment. NOTE: this includes a fourth additional patient when applicable. Dose-escalation/de-escalation decisions will be based on the occurrence of DLTs during Cycle 1 of the evaluated dose level and the recommendation of the Cohort Review Committee (CRC).
- If no DLTs are observed among the initial 3 (4 when applicable) patients of an evaluated dose level, the dose will be escalated for the following 3 patients.

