- Tumor types and corresponding treatment combinations to be evaluated will be identified prior to Phase IIA commencement with patients enrolled separately into tumor-specific arms of 20 patients each. This change will be documented in a protocol amendment before it occurs.
- The need for futility criteria to be evaluated in any of the arms following enrollment of a pre-defined number of patients < 20 shall be determined at a later date depending on tumor types evaluated. This change will be documented in a protocol amendment before it occurs.
- For all potential patients, there will be up to a 30-day screening and eligibility assessment period prior to enrollment.

All patients will continue to receive their assigned treatment throughout the study until the occurrence of disease progression, death, or other unacceptable treatment-related toxicity, or until the study is closed by the sponsor.

C1: Cycle 1; DLT: dose limiting toxicity; IO: immuno-oncology; RP2D: Recommended Phase II dose *MTD = one dose lower than discontinued dose

3.1.3 **Dose-limiting Toxicities**

A DLT will be defined as the occurrence of any of the following hematologic or non-hematologic AEs that are considered definitely, probably, or possibly related to IMSA101 in the first 28 days (first cycle) of treatment. The severity of AEs will be graded according to CTCAE v5.0. For safety run-ins for Phase IIA combination arms, DLTs will be defined as DLT-qualifying events considered at least possibly related to the drug combination, including AEs already characterized for the partner drug.

Hematologic AEs

- \geq Grade 4 neutropenia lasting for > 7 days
- Febrile neutropenia (defined as absolute neutrophil count (ANC) < 1000/mm³ with a single temperature of 38.3°C (101°F) or a sustained temperature of 38°C (100.4°F) for > 1 h)
- ≥ Grade 4 thrombocytopenia, or Grade 3 thrombocytopenia associated with Grade ≥ 2 bleeding
- \geq Grade 4 anemia

Non-hematologic AEs:

- Elevation of alanine transaminase (ALT) or aspartate transaminase (AST) by \ge 3X upper limit of normal (ULN) with concurrent elevation of serum total bilirubin \ge 2X ULN
- Any ≥ Grade 3 non-hematologic AE of any duration will be considered a DLT with the following exceptions:
 - Nausea/vomiting/diarrhea:
 - To be considered a DLT, ≥ Grade 3 nausea/vomiting/diarrhea must be refractory to supportive care and last > 3 days.
 - \geq Grade 3 nausea/vomiting/diarrhea that lasts \leq 3 days is not a DLT.
 - Fatigue:

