5.1 DESCRIPTION OF STUDY DAYS AND STUDY TREATMENTS

5.1.1 Screening/Baseline (Day -30 to Day 1)

- Obtain written informed consent before the start of any study-specific procedures.
- Review inclusion and exclusion criteria.
- Complete medical history including all previous cancer treatments.
- Record concomitant medications including start dates, indication, dose, and frequency.
- Record demographic data including year of birth, current age, age when informed consent is signed, gender, race, and smoking status.
- Measure and record height (cm) and weight (kg).
- Record vital signs (blood pressure, respiration rate, heart rate, body temperature).
- Perform full physical examination.
- Perform neurologic examination.
- Assess and record ECOG performance status (Appendix 13.1).
- Perform a 12-lead ECG.
- Collect blood samples for hematology tests (including coagulation parameters and CBC with differential) within 72 h prior to Cycle 1 Day 1.
- Collect blood samples for serum chemistry tests and creatinine clearance (using the Cockcroft-Gault formula, Appendix 13.3) within 72 hours of Cycle 1 Day 1.
- Urinalysis
- Perform a serum pregnancy test for female patients of childbearing potential.
- Radiographic assessments and, if applicable, photographic assessments of skin lesions will be performed by a formal photography vendor at the same time points as the radiographic assessments. Detailed instructions for photography will be included in a photography manual.
- Collect archival tumor tissue, if available (Phase I only).

5.1.2 **Cycle 1 Day 1 (± 0 Days)**

• Record concomitant medications taken since screening including start dates, indication, dose, and frequency within 72 h prior to Cycle 1 Day 1.

- Measure and record weight (kg) within 72 h prior to Cycle 1 Day 1.
- Record vital signs (blood pressure, respiration rate, heart rate, body temperature) within 72 h prior to Cycle 1 Day 1.
- Perform neurologic examination within 72 h prior to Cycle 1 Day 1.
- Assess and record ECOG performance status within 72 h prior to Cycle 1 Day 1 (Appendix 13.1).
- Perform a 12-lead ECG 30 to 60 minutes post-dose.
- PK blood samples (Phase I monotherapy only). Detailed instructions outlined in the laboratory manual.
- PD blood samples (Phase I monotherapy and combo therapy). Detailed instructions outlined in the laboratory manual.
 - 24 h post-dose sample will require patient to return to clinic on Cycle 1 Day 2.

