5.1.9 End of Study Visit (Safety Follow-up 30 days after Last Dose)

• Assess and record AEs.

5.1.10 **Cycle Extensions**

During this study, with the approval of the investigator and sponsor, a patient may be allowed a 2 week delay or extension between cycles. Rationale for delay or extension should be documented.

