6.6 SAFETY ASSESSMENTS

Safety assessments will include TEAEs, DLTs, vital signs, 12-lead ECG, physical examination, and laboratory safety evaluations. Toxicities will be graded according to CTCAE v5.0 criteria. Patients will be observed for 1 h in the clinic following intratumoral injections. In addition, following intratumoral injection on Day 1 of Cycle 1, patients will be admitted to the hospital for observation overnight.

Safety data will be listed by study site, patient number, and cycle. All TEAEs will be summarized by study phase and assigned dose. In addition, all SAEs, including deaths will be listed separately and summarized.

Grade 3 and 4 laboratory data will be summarized by study phase and assigned dose.

For patients who experience a DLT, data on AEs leading to treatment/study discontinuation will be listed.

Coagulation and urinalysis will be performed only at screening.

Safety evaluations (vital signs, ECOG assessment, and clinical laboratory studies) will be conducted at screening, Cycle 1 Day 1; baseline, then on Days 8 and 15 of Cycle 1, then Day 1 and Day 15 of every cycle thereafter for patients who continue treatment, or any time it is clinically indicated in the judgment of the investigator.

Neurologic examinations and ECOG performance status assessments (Appendix 13.1) will be performed at each study visit.

A complete standard 12-lead ECG recording (rhythm, VR, PR interval, QRS duration, QT and QTc) will be performed at screening, 30 minutes post-dose on C1D1, C1D8, C1D15, at EOT, and at any other visit where the investigator believes the assessment is indicated.

The following clinical laboratory tests will be performed:

• **Hematology** (blood sample with EDTA): hemoglobin, hematocrit, mean corpuscular volume, mean corpuscular hemoglobin, mean corpuscular hemoglobin concentration, white blood cell (WBC) count, WBC differential, red blood cell count, lymphocytes, monocytes, neutrophils, band neutrophils, eosinophils, basophils, platelets. The WBC differential may be automated or manual as per institutional standards. Reticulocytes should be done only when clinically indicated.

- Serum Chemistry (blood serum sample): Complete Serum Chemistry will include sodium, potassium, chloride, bicarbonate, blood urea nitrogen, creatinine, glucose, calcium, phosphate, magnesium, ALT, AST, alkaline phosphatase, total bilirubin, lactate dehydrogenase, total protein, albumin.

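### No hematology or chemistry test is required between the third Cycle 1 injection and nominal Day 29, one day after the DLT window closes, so capture of laboratory DLTs after that dose depends on visit timing and discretion

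*Combined protocol and SAP*

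**What the plan says.** - **DLT window.** Section 3.1.3 counts listed events "considered definitely, probably, or possibly related to IMSA101 in the first 28 days (first cycle) of treatment". Sections 3.1.4 and 6.1 and the synopsis define the MTD on the same 28 days, with at most 1 of 6 (or 7) patients having a DLT.
- **Cycle length and visits.** Section 10.2.2: "Each treatment cycle will be 4 weeks (28 days) in duration", and "There will be 3 clinic visits in Cycle 1 (Day 1, on Day 8, and Day 15". The three injections are given on those same days.
- **Laboratory tests.** After baseline, Section 6.6 places safety evaluations, including clinical laboratory studies, "then on Days 8 and 15 of Cycle 1, then Day 1 and Day 15 of every cycle thereafter", or whenever the investigator finds a clinical indication. Tables 1 and 2 and Sections 5.1.3 to 5.1.6 agree on hematology and chemistry. Section 5.1.11 also allows unscheduled visits with any assessment.
- **Timing tolerance.** Cycle 2 Day 1 has a window of 3 days either way (Table 1 footnote 14, Table 2 footnote 11). Section 5.1.10 adds that "a patient may be allowed a 2 week delay or extension between cycles".
- **Escalation.** Section 3.1.1: "No dose escalation decisions will be made until all patients in a dose level complete the first 28 days of treatment". Section 3.3 has the Cohort Review Committee look at all the safety data available to it.

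**The concern.** Several DLTs in Section 3.1.3 are detected by a blood test: Grade 4 thrombocytopenia or anemia, Grade 4 neutropenia lasting more than 7 days, raised ALT or AST together with raised bilirubin, and non-hematologic laboratory events of Grade 3 or higher. The last group counts whatever its duration, so a brief, silent abnormality qualifies but has to be sampled to be seen. Section 1.5 anticipates changes of this type, including lower platelets and hemoglobin and higher ALT and AST.

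The primary endpoint, the MTD/RP2D, rests on the Cycle 1 DLT count with a cut-off between 1 and 2 events in 6 patients, so one unseen event can change a cohort's result. The third dose also matters to evaluability: Section 4.1 ties replacement of early dropouts to not having received all three doses. Yet no laboratory follow-up of that dose is required inside the window on the nominal schedule.

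**Working it through.** The plan states no DLT rate or operating characteristic, so there is no figure of its own to reproduce. The check is day arithmetic, followed by an illustration on assumed rates.

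**1. Where the next test falls.** Cycle 2 Day 1 = 28 + 1 = Day 29. With the visit window: 29 − 3 = Day 26 to 29 + 3 = Day 32. With a 2-week extension: 29 + 14 = Day 43, or Day 46 with the window. Of the seven permitted days without an extension, three (26, 27, 28) lie inside the DLT window and four (29 to 32) outside.

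**2. Time after the third dose.** Nominally the dose is on Day 15, leaving 28 − 15 = 13 days of window (Days 16 to 28). With that visit's own window (Days 12 to 18) the range is 28 − 18 = 10 to 28 − 12 = 16 days. From dose 3 to the next scheduled panel is 29 − 15 = 14 days nominally, and from 26 − 18 = 8 to 32 − 12 = 20 days with both windows.

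**3. Whether another draw covers the gap.** Section 5.1.4 lists the Day 15 draw ahead of the injection without stating its timing; a same-day sample could show only same-day effects of dose 3. The extra Cycle 1 return visit (Section 5.1.2: "24 h post-dose sample will require patient to return to clinic on Cycle 1 Day 2") follows the first dose and serves pharmacodynamics. No PK or PD blood is drawn between Cycle 1 Day 15 and Cycle 2 Day 1.

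**4. Two related consequences.** In the primed combination levels, Day 1 is the lower priming dose and the full dose is given on Days 8 and 15, so nominally only one of the two full doses is followed by an in-window panel. Also, the nominal Day 8 and Day 15 tests are exactly 7 days apart, so those two tests alone cannot show Grade 4 neutropenia lasting more than 7 days.

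**5. Effect on the decision rules.** Assume a true DLT rate p and a share m missed; the counted rate is q = p(1 − m).

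- MTD rule: P(≤1 of 6) = (1 − q)^6 + 6q(1 − q)^5.
- 3+3 escalation: (1 − q)^3 + 3q(1 − q)^2 × (1 − q)^3.
- Run-in: P(≤1 of the first 5 and ≤3 of 10).

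| p | m | q | P(≤1 of 6) | 3+3 escalates | Run-in passes |
|---|---|---|---|---|---|
| 30% | 0 | 0.300 | 0.420 | 0.494 | 0.464 |
| 30% | 10% | 0.270 | 0.487 | 0.557 | not computed |
| 30% | 25% | 0.225 | 0.594 | 0.654 | 0.650 |
| 30% | 50% | 0.150 | 0.776 | 0.814 | 0.824 |
| 40% | 0 | 0.400 | 0.233 | 0.309 | 0.248 |
| 40% | 25% | 0.300 | 0.420 | 0.494 | 0.464 |
| 40% | 50% | 0.200 | 0.655 | 0.709 | 0.711 |

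**6. An uncounted DLT is not the same as a changed decision.** If a share s of patients had a silent uncounted DLT, the chance of at least one among 6 is 1 − (1 − s)^6: 26%, 47% and 74% for s = 5%, 10% and 20%. The 6-patient result changes only if the counted total is at most 1 and the true total at least 2. With 10% of patients having a counted DLT, independently of silent ones, the true rate is r = 1 − 0.90(1 − s), or 0.145, 0.19 and 0.28. The chance of a changed result is P(≤1 of 6 at 0.10) − P(≤1 of 6 at r):

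- s = 5%: 0.886 − 0.788 = 0.10
- s = 10%: 0.886 − 0.680 = 0.21
- s = 20%: 0.886 − 0.464 = 0.42

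All values of p, m and s, and the 10% counted rate, are assumptions.

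**The case against.** A reader might infer that a laboratory DLT after the third dose cannot enter the count at all. The documents do not support that. Cycle 2 Day 1 may fall on Days 26 to 28, inside the window; clinically indicated and unscheduled tests are allowed throughout; and anything they find counts. What stands is that none of these is required, and discretionary testing is unlikely to reveal a silent abnormality.

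A reader might also infer that an abnormality first seen on Day 29 is assigned to Cycle 2 and lost. Section 3.1.3 defines a DLT by its occurrence in the 28 days, not by the date it is detected. Section 5.1.5 lists the Cycle 2 Day 1 draw before the injection, so such a finding would follow Cycle 1 doses only. The committee reviews all available safety data, and the RP2D may be set below the MTD. That is fair, but the plan neither says how such a finding is attributed nor requires the result to be available before the decision.

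Other mitigating points: the Day 8 and Day 15 panels each follow an injection, at the same dose as the third in unprimed cohorts; Section 1.3.3 reports no accumulation in animals; the half-life in mice was about 10 to 15 minutes; Section 1.5 describes most nonclinical laboratory changes as minimal to mild; and patients stay overnight after the first dose. These make a large effect less likely. They do not supply a test after the third dose.

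**Conclusion.** The gap is real and lies in the measurement behind the primary endpoint. For a patient who continues treatment, capture of a laboratory DLT after the third injection depends on an early Cycle 2 Day 1 visit or a discretionary test, so the same toxicity could count at one site and not at another. A patient who stops has an end-of-treatment panel (Section 5.1.8), but its date is not tied to Day 28.

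The direction of the bias is clear: fewer DLTs counted, and a higher chance of passing a dose that the 1-of-6 rule would fail. The size is unknown, because the documents give neither a DLT rate nor the share that is laboratory-only and follows the third dose. The calculated figures show sensitivity and are not estimates. In particular, the 26% to 74% range is the chance of an uncounted event, not of a wrong dose decision. The 13 of 28 days (46%) without a required test measures time, not missed toxicity. The Phase IIA run-ins follow the same laboratory schedule (Table 2) and carry the same weakness. This should be fixed, but it does not by itself invalidate the escalation design.

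**What to change.** Reconcile the laboratory schedule (Tables 1 and 2, Sections 5.1.5 and 6.6) with the DLT window, the MTD definition and the escalation timing (Sections 3.1.1, 3.1.3, 3.1.4 and 6.1, and the synopsis), in all of these places together. Changing only the DLT and escalation sections would leave the 28-day wording in the MTD definition and create a new conflict. The reconciled text should:

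- make the already scheduled Cycle 2 Day 1 results, stated to be pre-dose, part of the Cycle 1 DLT assessment, and say how an abnormality first found there is attributed;
- use the end-of-treatment panel for patients who do not start Cycle 2;
- require these results to be available before the Cohort Review Committee decides;
- say how this works when Cycle 2 is delayed, since 28 days and first cycle may then no longer mean the same period and the assessment length could differ between patients;
- apply equally to the Phase IIA run-ins.

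No new blood draw or visit is needed. The cost is a wait of a few days before the escalation decision, longer when Cycle 2 is delayed, and a DLT count that may be slightly less favourable.
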